### REVISION CHRONOLOGY:

Date	Version	Change(s) since last version
01-03-2021	Original (version 1.0)	N/A
21-03-2021	Version 2.0	Adjusted the protocol based on the comments received from PRC. The PRC comments and

		
revisions are provided on the portal.

28-03-2021	Version 3.0	

1) Added objective for exploratory analysis of physician profile and treatment.

2) Clarified second secondary objective in section 4.43 on how to proceed with the analysis.

3) In section 3.2.2 clarified the routine laboratories results that will be collected in the prospective and retrospective.

28/06/2021	Version 4.0	

1) On page 1 the title on the header should be written as “Non-interventional Study Protocol”

2) For the protocol synopsis on page 9 the correct title is “LUNELORD: A descriptive, prospective study to assess demographic, pharmacologic, biomarker, clinical features and QoL of patients with LUpus NEphritis and Long-term ORgan Damage.”

3) In Appendix 5 on page 48 the title should be “LUNELORD: A descriptive, prospective study to assess demographic, pharmacologic, biomarker, clinical features and QoL of patients with LUpus NEphritis and Long-term ORgan Damage.”

4) Added clarification for inclusion criteria.

Copyright 2021 the GlaxoSmithKline group of companies. All rights reserved.  
Unauthorised copying or use of this information is prohibited

## ABBREVIATIONS

ACR	American College of Rheumatology
ADARRC	Advanced Academic Rheumatology Review Course
AE	Adverse event
anti-dsDNA	Antibody to double-stranded DNA test
Anti-Rib	Antibody to ribosomal P protein
Anti-Scl-70	Anti-topoisomerase I antibody
anti-Sm	Antibody smooth muscles
anti-U1-RNP	Anti-ribonucleoprotein
ARA	American Rheumatism Association
ASE	All subjects enrolled
C3/C4	Complement components 3 and 4
CI	Confidence interval
CRO	Clinical research organisation
eCRF	Electronic case report form
eGFR	Estimated glomerular filtration rate
ESR	Emirates Society for Rheumatology
ERA-EDTA	European Renal Association-European Dialysis and Transplant Association
ESRD	End-stage renal disease
EULAR	European League against Rheumatisms
GFR	Glomerular filtration rate
GP1	anti-beta 2 glycoprotein 1
GPP	Good Pharmacoepidemiology Practice
GSK	GlaxoSmithKline
HCRU	Healthcare resource utilisation
HIV	Human immunodeficiency virus
HRQoL	Health-related quality of life
ICU	Intensive care unit
IEC	Independent ethics committee
IHD	Individual human data
IRB	Institutional review board
ISN/RPS	International Society of Neurology and the Renal Pathology Society
KAR	Kuwait Association of Rheumatology
LN	Lupus nephritis
MRI	Magnetic resonance imaging
NSAID	Non-steroidal anti-inflammatory drug
ORS	Orthopaedic Research Society
PPPF	Physician practice profile form
QoL	Quality of life
SAP	Statistical analysis plan
SDI	SLICC/ACR damage index
SELENA	Safety of estrogens in lupus national assessment
SF-36	36-item short form health survey
SLE	Systemic lupus erythematosus
SLEDAI	Systemic lupus erythematosus disease activity index

SLEDAI-2K	Systemic lupus erythematosus disease activity index 2000
SLICC	Systemic Lupus International Collaborative Clinics
sPVP	Specific pharmacovigilance plan
TNF	Tumour necrosis factor
UPCR	Urinary protein to creatinine ratio
WHO	World Health Organisation

## TRADEMARK INFORMATION

Trademarks of the GlaxoSmithKline group of companies	Trademarks not owned by the GlaxoSmithKline group of companies
Belimumab (Benlysta®)	36-Item Short Form Health Survey (SF-36): used with the permission of RAND corporation  SLEDAI-2K from Gladman DD, Ibañez D, Urowitz MB. Systemic lupus erythematosus disease activity index 2000. J Rheumatol. 2002;29(2):288-91. PMID: 11838846.

## PROTOCOL SUMMARY

Title	LUNELORD: A descriptive, prospective study to assess demographic, pharmacologic, biomarker, clinical features and QoL of patients with LUPUS NEphritis and Long-term ORgan Damage
Rationale	
Systemic lupus erythematosus (SLE) is a potentially serious, chronic, autoimmune disease, which can affect multiple organs of the body, including the kidneys (lupus nephritis). The high variability and its unpredictable course (flaring/remission), combined with a lack of indicated and integrated treatments, induce a high unmet need within the patient population. Reliable data on LN-related care patterns and resource utilisation in 5 countries in Arabian Gulf (UAE, Kuwait, Qatar, Bahrain, and Oman) region are currently unavailable.
 
The expected key outcomes of this study will be:
 
 
• Description of clinical characteristics, demographics, and health-related quality of life (HRQoL) of LN patients.
 
• Description of “real-world” standard of care and healthcare resource utilisation (HCRU) associated with LN in the Gulf countries: Bahrain, Kuwait, Oman, Qatar, and United Arab Emirates.
 
 
The information collected may be used for scientific communication among the expert/physician community and payers with the aim to enhance medical care of lupus nephritis. The study protocol is designed to obtain an accurate, “real-world” picture of LN patients in the Gulf countries.

Study Objectives	
 
• Primary: Describe demographics, clinical characteristics, comorbidities, treatments and HRQoL of LN patients across 5 Gulf countries.
 
• Secondary: 
 
◦ Describe refractory LN cases, involving rituximab, and to assess changes in serological markers of disease activity (including autoantibodies and complement levels) over the treatment period.
 
◦ Assess the association between clinical factors, biomarkers, treatment and renal remission.
 
◦ Assess impact of LN on HRQoL over a one-year period after diagnosis or enrolment.
 
◦ Describe LN HCRU and direct medical cost, associated with LN management across 5 Gulf countries over a one-year period.
 
◦ Exploring the difference in treatment patterns by physician profile (physicians in private versus public hospitals).
 
 
 

Study Design	
This is a multicentre prospective study with a patient-completed survey and retrospective chart review component.
 
This study will enrol approximately 200 patients with clinician diagnosed LN cases.
 
Staff at participating sites will review their LN patients' medical charts to identify potentially eligible patients who meet the study's preliminary selection criteria. Identified patients who are potentially eligible will be contacted by trained site staff via phone, or approached onsite at the patient's routine care visit, if the visit falls within the study enrolment timelines. When approaching the patient, site staff will review the main study informed consent form (ICF) with patients, explain the study purpose and design, which will include a prospective survey as well as a one-time retrospective data abstraction from their medical chart. Additionally, site staff will answer any questions patients may have about the study. Patients will be asked to confirm their consent to participate in the study by signing the informed consent.
 
 
• A retrospective phase to collect data from diagnosis or up to one year before enrolment, and
 
• A prospective arm consisting of 5 visits as per routine care of a LN patient: 
 
◦ Visit 1: enrolment
 
◦ Visit 2: 3-month follow-up after Visit 1
 
◦ Visit 3: 6-month follow-up after Visit 1
 
◦ Visit 4: 9-month follow-up after Visit 1
 
 
 

	
 
○ Visit 5: last 12-month follow-up visit after Visit 1
 

Study Population	
 
● Inclusion criteria: 
 
○ ≥age of 18 years
 
○ Clinician diagnosed LN patient per physician's discretion
 
○ At least one visit to the investigational centre, recorded in medical documentation, during the past (12) twelve months prior to enrolment date
 
○ Literacy in English or Arabic allowing to fully comprehend the written informed consent and study-specific patient reported questionnaires
 
○ Written informed consent by the patient
 
 
 
● Exclusion criteria: 
 
○ Incomplete medical records to be able to assess the disease severity or absence of any of the following renal laboratory results from the medical record within the last (12) twelve months: 
 
○ Urinary protein to creatinine ratio (UPCR) or 24-hour proteinuria or urine sediment (activity)
 
○ Serum creatinine or estimated glomerular filtration rate (eGFR); or measured glomerular filtration rate (GFR), if eGFR is not available
 
 
 
○ Current or medical history of: 
 
○ Congenital or acquired immunodeficiency
 
○ Malignancy in active treatment phase
 
○ Acute viral infection, such as HIV infection, requiring hospitalisation
 
 
 
 
 

Study Duration	
 
● Retrospective arm: medical chart review from diagnosis or up until 12 months prior to enrolment
 
● Prospective arm: 12 months after enrolment
 

Data Collection	
 
● Retrospective data collection - medical chart review from diagnosis or up till 12 months prior to enrolment 
 
○ Basic patient demographic characteristics (gender, race/ethnicity, BMI, date of first SLE manifestation, date at SLE diagnosis, date at first LN manifestation, date at LN diagnosis, date at last visit in 2020)
 
○ LN/SLE treatment medications, including starting dose, current dose, date of treatment start and end, dose at cessation and reasons for medication choice (medications limited to NSAIDs, antimalarials, corticosteroids, immunosuppressants/cytotoxics and biologics)
 
○ LN treatment history (most recent induction regimen, number of prior treatment failures/relapse(s) [if any], ESRD, and dialysis [current/past and type], listed for transplant/prior transplant conducted)
 
○ Most recent LN classification including class and histological activity/chronicity based on most recent biopsy (International Society of Neurology and the Renal Pathology Society [ISN/RPS] or World Health Organisation [WHO] classification)
 
○ LN clinical manifestations
 
○ Comorbidities (such as antiphospholipid syndrome/thrombotic microangiopathy, obesity, cardiovascular disease, diabetes)
 
○ Renal laboratory assessments (such as UPCR or 24-hour proteinuria or urine sediment [activity], serum creatinine, and eGFR or measured GFR, if eGFR is not available)
 
○ Most recent serological findings (such as anti-phospholipid antibodies [anticardiolipin, anti-beta 2 glycoprotein 1 [GP1] and lupus anticoagulant], anti-C1q, low-complement [C3/C4] and positive anti-double-stranded-deoxyribonucleic acid [anti-dsDNA])
 
○ Other laboratory tests (haematology, liver function tests, lipid profile, and plasma albumin)
 
○ Active non-renal clinical manifestations of SLE (such as mucocutaneous, central nervous system, constitutional, cardiopulmonary, gastrointestinal, hematologic, musculoskeletal, vasculitis)
 
○ Most recent total Systemic Lupus Erythematosus Disease Activity Index (SLEDAI), such as SLEDAI or SLEDAI-2K
 
 
 

	
 
○ Renal remission defined as proteinuria of <0.7 g/d or <0.5g/d or per physicians' discretion
 
● Prospective data collection from enrolment or diagnosis of LN (0, 3, 6, 9, 12 months) 
 
○ HRQoL using 36-Item Short Form Health Survey (SF-36) at enrolment (Visit 1) and at 12 months of follow-up (Visit 5)
 
○ Clinical manifestations at period start with clinical improvement/ worsening assessment at period end
 
○ Changes in disease activity assessment tools used
 
○ Any cases presented with refractory LN (defined as inefficacy of cyclophosphamide, use of rituximab, splenectomy, or inefficacy of ≥2 immunosuppressives (methotrexate, leflunomide, abatacept, anti-TNF, azathioprine, mycophenolate mofetil, and/or mycophenolic acid))
 
○ Renal remission identified (defined as proteinuria of <0.7 g/d or <0.5g/d or per physicians' discretion)
 
○ Biopsies requested
 
○ Changes linked to the primary treatment of the disease
 
○ Renal laboratory assessments (such as UPCR or 24-hour proteinuria or urine sediment [activity], serum creatinine and eGFR or GFR, if eGFR is not available)
 
○ Most recent serological findings (such as anti-phospholipid antibodies [anticardiolipin, GP1 and lupus anticoagulant], anti-C1q, low complement [C3/C4] and positive anti-dsDNA)
 
○ Other laboratory tests (haematology, liver function tests, lipid profile, and plasma albumin)
 
○ HCRU (number of laboratory tests, number of dialyses and use of imaging techniques, ICU hospitalisations/hospitalisations, outpatient visits)
 
 
 

Statistical Methods	
Continuous numeric variables will be summarised using the mean, ±standard deviation, median, interquartile range, minimum and maximum. Categorical variables will be summarised using frequency distributions.
 
 
● Primary objective: summary statistics will be used to describe patient profile, demographic features, clinical manifestations, comorbidities, severity, treatments and HRQoL of LN patients across 5 Gulf countries.
 
● Secondary objective 1: summary statistics will be used to describe refractory LN cases and the independent t-test or Wilcoxon signed rank test along with repeated measures analysis will be used to test for changes in serological markers of disease activity at one year and over the treatment period. Changes in categorical variables at one-year period will be tested using the McNemar's test.
 
● Secondary objective 2: univariate and multivariate logistic regression with renal remission as the dependent variable and clinical factors and treatment as the independent variables. Odds ratios and 95% confidence intervals (CIs) will be presented.
 
● Secondary objective 3: paired t-test on the HRQoL scores at enrolment and at one year, or Wilcoxon signed rank test for non-normal distribution. Repeated measures will be used to assess changes over time.
 
● Secondary objective 4: for each country, the average HCRU and direct medical cost will be estimated along with its 95%CI.
 
● Secondary objective 5: Exploratory analysis of the differences between physician profile and treatment.
 

Sample Size and Power Calculations	200 patients, a statistical test will ensure the sample size calculation is powered to generate the data. The sample size calculation was computed by PASS® version 2019.

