As for the treatment of LN, it depends on disease severity and risk for progressive kidney damage (3). A conservative treatment is used for the non-proliferative forms of LN (class II and V with sub-nephrotic range proteinuria and normal glomerular filtration rate), with treatment focused on blood pressure control with renin-angiotensin system blockade and immunomodulation with antimalarials (e.g. hydroxychloroquine) (3). As for immunosuppressive agents, these are used as needed to treat extrarenal manifestations only. In addition to antimalarials and renin-angiotensin system blockade, proliferative forms of LN (class III, IV, or III/IV+V) and class V with nephrotic syndrome are treated with systemic immunosuppression combined with high-dose corticosteroids to suppress inflammation and control autoimmunity (3). This induction phase of treatment generally lasts 3–6 months and is followed by a prolonged, but less intense maintenance phase, often lasting years. It is not clear when maintenance therapy can be withdrawn. A repeat kidney biopsy showing histologic remission during maintenance in LN patients who have achieved complete clinical remission, or who have stable but persistent proteinuria, may help in making a decision to taper off therapy (4). During the maintenance phase, immunosuppressive/cytotoxic agents are continued but de-escalated slowly over time to limit risk for LN flares. Biological drugs developed more recently show interesting beneficial effects in LN (4). They decrease the level of B lymphocytes which contributes to the decrease in autoantibodies known to play the central role in disease activity and consequently decrease the global inflammation level (15).

There is a paucity of data in the Gulf countries on LN care management (treatment strategies, healthcare pathways, healthcare resource utilisation [HCRU] and costs), especially in moderate and severe cases. In this context, GSK has decided to carry out an observational study mainly to characterise LN patients in 5 Gulf countries who may benefit from early intervention. Also, in order to have an accurate estimation of the costs of LN care management. This study aims at evaluating disease costs according to patients' profile.

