#### 4.4.3. Secondary Analysis

The first secondary objective is to describe refractory LN cases, involving rituximab, and to assess changes in serological markers of disease activity (including anti-nuclear antibody, anti-dsDNA antibody and complement levels) over the treatment period. This will be achieved by first using summary statistics as per the general consideration of data analysis section at each time point. To assess one-year changes in numeric variables, the paired t-test or Wilcoxon signed rank test will be used while the McNemar's test will be used for changes in categorical variables. In addition, repeated measures analysis will be used to look at changes over the whole time period.

The second secondary objective is to assess the association between clinical factors (disease activity), biomarkers (inflammatory markers and hematological markers), treatment (type and duration of therapy) and renal remission. The variables included in the model will be taken from the measures closest to the time of enrolment. For continuous variables, the nonparametric Wilcoxon test will be used for assessing differences between the patients who attained renal remission versus patients who did not attain renal remission, while the chi-square test will be used for dichotomized variables. Statistically significant factors will be included in the multivariate logistic regression models with renal remission as the dependent variable. Odds ratio and corresponding 95% confidence intervals (CIs) will be presented.

The third secondary objective is to assess impact of LN on HRQoL over a one-year period after diagnosis or enrolment. This will be achieved by looking at changes in the SF-36 physical and mental components, and the total score at one year using the paired t-test or Wilcoxon signed rank test for non-normal distribution. Changes over all the time period will be assessed using repeated measures analysis.

The fourth secondary objective is to estimate HCRU and direct medical cost, associated with LN management across 5 Gulf countries over a one-year period. This will be carried out as per [Section 4.5. Cost Evaluation](#). Generating an estimate for the average HCRU and direct medical cost and creating the 95% CIs for those will be carried out for each country.

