4.5. Specific Analyses

4.5.1. Analysis of the primary objective

Patient demographics will be summarised using the methods presented in the general consideration section (see Table 1). Similar analysis will be done for the clinical manifestations, comorbidities, severity, treatments and HRQoL of LN patients over one year (Tables 2-5).

4.5.2. Analysis of secondary objective 1

Summary statistics will be used to describe refractory LN cases and the independent t-test or Wilcoxon signed rank test along with repeated measures analysis will be used to test for changes in serological markers of disease activity at one year and over the treatment period. Changes in categorical variables at one-year period will be tested using the McNemar's test (see Table 6).

4.5.3. Analysis of secondary objective 2

Univariate and multivariate logistic regression with renal remission as the dependent variable and clinical factors and treatment as the independent variables. Odds ratios and 95% confidence intervals (CIs) will be presented. Variables with a p-value of 0.25 or less along with known associated factors with renal remission will be used to build the final multivariate model. The final multivariable model will contain only significant factors or those who have confounding effect on others in the model.(see Table 7).

4.5.4. Analysis of secondary objective 3

Changes in SF-36 total score from baseline to one year will be test for significance using the paired t-test (or Wilcoxon signed rank test for non-normal distribution. The same analysis will be done for all subscales of the SF-36 (see Table 8).

4.5.5. Analysis of secondary objective 4

For each country, the average HCRU and direct medical cost will be estimated along with its 95%CI (see Table 9).

4.5.6. Analysis of secondary objective 5

CCI

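### Treatment odds ratios for renal remission are open to confounding by indication, because no adjustment set with LN class and disease duration is pre-specified

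*Protocol*

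**What the plan says.** **How treatment is chosen.** Protocol section 1 states: "As for the treatment of LN, it depends on disease severity and risk for progressive kidney damage". It describes conservative care for non-proliferative forms, and adds that "proliferative forms of LN (class III, IV, or III/IV+V) and class V with nephrotic syndrome are treated with systemic immunosuppression" together with high-dose corticosteroids. The SAP background repeats this.

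**The model in the protocol.** The Protocol Summary (Statistical Methods, secondary objective 2) plans "univariate and multivariate logistic regression with renal remission as the dependent variable and clinical factors and treatment as the independent variables". Section 4.4.3 gives the candidates as "clinical factors (disease activity), biomarkers (inflammatory markers and hematological markers), treatment (type and duration of therapy) and renal remission", measured closest to enrolment. Its entry rule is: "Statistically significant factors will be included in the multivariate logistic regression models with renal remission as the dependent variable".

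**The model in the SAP.** SAP 4.5.3 is wider. It starts from variables with a univariate p-value of 0.25 or less, plus factors already known to be associated with remission, which it does not list. It then says: "The final multivariable model will contain only significant factors or those who have confounding effect on others in the model". The shell in SAP Table 7 shows age, gender, treatment and SLEDAI-2K, with an open row.

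**What is available.** LN class from the most recent biopsy, date of LN diagnosis and renal laboratory values are all in the data collection (Protocol 3.2.2). SAP Table 2 summarises LN class and time since LN diagnosis, but only descriptively. The Limitations section of the protocol does not mention confounding by indication.

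**The concern.** If regimen depends on class and severity, and these also affect the chance of remission, a treatment odds ratio from a model without them mixes the regimen with the kind of patient who receives it. If the patients given stronger regimens are less likely to remit, a useful regimen can look neutral and a neutral one harmful. For rituximab the link is built in, because Protocol 3.2.2 counts its use as one of the criteria for refractory disease.

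SLEDAI-2K, the one severity measure named in Table 7, is not a clean substitute. It has renal items, but its proteinuria item (above 0.5 g per 24 hours, Appendix 2) overlaps the outcome.

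Table 7 would show the result as an adjusted odds ratio by treatment, and Protocol 1.1 foresees use of the findings with payers and in clinical management. The planned power is also at stake: the headline calculation takes treatment as unrelated to every other covariate, which does not fit the protocol's account of how treatment is chosen.

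**Working it through.** **1. The plan's own figure.** Inputs from Protocol 3.3.2 and Table 1: N = 200, share with X = 1 B = 0.35, P0 = 0.200, odds ratio 2.508 (P1 = 0.385), R² = 0, alpha 0.05. The text attaches the 35% to remission; Table 1 attaches it to X, and that reading reproduces. With P̄ = 0.65 × 0.200 + 0.35 × 0.385 = 0.265, the formula for one binary X is

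N = [1.96·√(P̄(1−P̄)/B) + 0.84·√(P0(1−P0) + P1(1−P1)(1−B)/B)]² / [(P1−P0)²(1−B)(1−R²)].

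This gives N = 200.04 and power 0.7999 (two-sided). The stated 80% is correct at R² = 0.

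**2. Assumptions that the documents do not give.** Half the patients are proliferative. The regimen is used by 55% of them and 15% of the others, so 0.5 × 0.55 + 0.5 × 0.15 = 35% overall, as in Table 1. Remission off the regimen is 0.20. The odds ratio for remission in proliferative class is 0.3 to 0.5.

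**3. Treatment-only model, class odds ratio 0.4.**
- Proliferative share among treated: 0.275/0.35 = 0.786. Among untreated: 0.225/0.65 = 0.346.
- Untreated remission of 0.245 (other) and 0.115 (proliferative) averages 0.654 × 0.245 + 0.346 × 0.115 = 0.20.
- With a true odds ratio of 2.508, treated remission is 0.449 and 0.246. The average is 0.214 × 0.449 + 0.786 × 0.246 = 0.289.
- Observed odds ratio: (0.289/0.711)/0.25 = 1.63. Power in step 1's formula falls to 30%.
- With a true odds ratio of 1.0, treated remission is 0.214 × 0.245 + 0.786 × 0.115 = 0.143, and the observed odds ratio is (0.143/0.857)/0.25 = 0.67.

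A small part of the drop from 2.508 is not confounding, because odds ratios shrink when any prognostic factor is left out. With equal use in both classes, untreated remission would be 0.271 and 0.129, treated 0.482 and 0.271 (mean 0.377), and the crude odds ratio 2.42. The fall from 2.42 to 1.63 is due to channelling.

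**4. Range and selection rule.** True odds ratio 2.508, 55%/15% use, samples of 200, class offered as a candidate where the row says so:

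| Model | Treatment odds ratio, class odds ratio 0.3 to 0.5 |
|---|---|
| Class absent | about 1.4 to 1.8 |
| Class entered only if univariate p < 0.05 (Protocol 4.4.3) | about 1.9 to 2.1 (median) |
| Class forced in | about 2.5 |

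The protocol's screen admits class in only about 12% to 63% of samples, because a helpful regimen given mainly to proliferative patients masks the class effect in the univariate test. The treatment term was kept throughout; under the protocol's rule it would also have to pass its own screen. Over weaker or stronger channelling (45%/25% to 60%/10%), the class-absent odds ratio runs from 1.23 to 2.11.

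**5. A second illustration.** Take 50% remission, 35% treated, true odds ratio 1.0, and class multiplying the odds of treatment by 2 to 8. In four scenarios at N = 200, the false-positive rate for treatment was 6% to 39% without class and about 4% to 5% with it.

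**6. Price of adjustment.** Under step 2, R² of treatment on class is 0.5 × 0.5 × (0.55 − 0.15)²/(0.35 × 0.65) = 0.18, close to the 0.2 row of Table 1. Power for 2.508 at R² = 0.2 is 0.71, and 0.59 at 0.4. Table 1 puts the detectable odds ratio at 80% power at 2.770 and 3.199.

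**The case against.** The strongest reply is that the SAP already covers this. It admits known associated factors apart from the p-value screen, and it keeps a term that is significant or that confounds another. A reader might infer that class would often be dropped, since a class odds ratio of 0.5 reaches significance in only about 53% to 68% of studies of this size. That tests half of an either/or rule. With class in the model and an assumed 10% change-in-estimate criterion (the SAP gives none), class stays in about 88% to 99% of samples and the treatment odds ratio is close to the truth. This part of the objection stands. What remains is that candidates and criterion are unnamed, and that the protocol's rule is narrower and would often screen class out.

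Three further points stand in part:
- The documents say how classes are treated, not how often they remit, so the direction and size of the bias are assumed. The figures also come from models without age, gender and SLEDAI-2K; the bias left after those terms has not been calculated.
- The objective is worded as association. That limits the claim, but an adjusted odds ratio by treatment still invites comparison of regimens.
- Forcing in earlier proteinuria and eGFR could do harm. Appendix 1 collects data only if available, eligibility accepts urine sediment in place of quantified proteinuria, and analysis is listwise. Therapy may also have begun before those values were taken, so they could already reflect treatment. The same timing caution applies, less sharply, to class from the most recent biopsy.

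**Conclusion.** The point holds in a limited form. The protocol ties treatment to class and severity, and neither document requires LN class or disease duration in a model that reports treatment odds ratios. Those odds ratios are open to confounding by indication. A reader might go further and say that they are confounded; the documents do not support that, because the outcome depends on a final covariate set that the SAP leaves open.

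Under the stated assumptions the loss is material: roughly 1.4 to 1.8 in place of 2.508 if class is absent, and 1.9 to 2.1 under the protocol's rule. These sizes are illustrative. Independently of them, the 80% power for 2.508 applies only if treatment is unrelated to the other covariates. The change should be made before analysis. It does not affect the primary descriptive objective.

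**What to change.** In Protocol 4.4.3 and SAP 4.5.3, use one rule: every model with a treatment term keeps the following, whatever their p-values:
- LN class in three levels: proliferative (III/IV, with or without V), other, and no biopsy. The third level stops listwise deletion from removing patients without a biopsy.
- Time since LN diagnosis.

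Add earlier proteinuria and eGFR or creatinine only as a sensitivity analysis, using values measured before the treatment started where these exist. Add rows for the forced terms to Table 7, and describe the treatment odds ratios there and in the report as associations. In Protocol 3.3.2 and SAP 3.2, quote the detectable odds ratio from a row with R-squared above zero (2.770 at 0.2, 3.199 at 0.4).

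The cost is wording and somewhat wider intervals. The forced variables are already in the data collection plan.
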